Data Set Name	
HA_disp_analysis_long.sas7bdat
 
HA_disp_monthly_analysis_set.sas7bdat

Code Location	OCHIN archive server

A Cohort Study of Public Health Insurance Coverage Loss among Oregon Adolescents

Full Citation	Angier, H., C. J. Tillotson, L. S. Wallace, M. Marino, J. P. O' Malley, A. Sumic, L. Baker, C. Nelson, N. [name], A. Suchocki, H. Holderness and J. E. DeVoe (2018). A Cohort Study of Public Health Insurance Coverage Loss among Oregon Adolescents. J Health Dispar Res 11(1).
Objective	The purpose of this study was to identify the sociodemographics of adolescents transitioning to young adulthood who lost public health insurance which could inform future health policies for this vulnerable population.
Study Population	Oregon adolescents (17-19 years of age) with public coverage [January 1, 2011-December 31, 2013 (n=51,988)].
Exclusion Criteria	Missing information on urban/rural residency status (n=4,025) and/or family income (n=973).
Independent Variables	Sociodemographic characteristics: age, sex, race, ethnicity, language, percentage of federal poverty level based on family income and size, history of a healthcare visit to a community health center included in the OCHIN network during the study period (2011-2013), and urbanicity.
Dependent Variables	OHP Coverage
Covariates	
Analysis Plan	Time to Event: to determine association of coverage loss with sociodemographic characteristics.
Data Set Name	analysis_nogaps_01202016.sas7bdat dmapochin13_nogaps_01202016.sas7bdat Code is under: R:\Active projects\IMPACCT\Reports\Data analysis and results\Teen Transition\[name]\SAS Code and Programs\5d_MV Models nogaps 01112016.sas
Code Location	OCHIN archive server

A New Role for Primary Care Teams in the United States After “Obamacare”: Track and Improve Health Insurance Coverage Rates.

Full Citation	DeVoe, J. E., H. Angier, M. Hoopes and R. Gold (2016). A New Role for Primary Care Teams in the United States After “Obamacare”: Track and Improve Health Insurance Coverage Rates. Family Medicine and Community Health 4(4): 63-67(65).
Objective	Describe efforts to longitudinally track health insurance rates using data from the electronic health record (EHR) of a primary care network and to use these data to support practice-based insurance outreach and assistance.

Study Population	OCHIN member clinics and patients.
Exclusion Criteria	Not an OCHIN member clinic or patient.
Independent Variables	NA

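### Adolescent coverage-loss study: CHC visit history is measured over the same 2011-2013 window as the outcome, so a fixed yes/no covariate gives a biased hazard ratio if losing coverage changes visiting

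*Combined protocol and SAP*

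**What the plan says.** All of this is in the combined protocol and SAP, Data Analyses, in the entry on public coverage loss among Oregon adolescents.

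- Study Population: "Oregon adolescents (17-19 years of age) with public coverage [January 1, 2011-December 31, 2013 (n=51,988").
- Objective: to "identify the sociodemographics of adolescents transitioning to young adulthood who lost public health insurance", as input to health policy.
- Dependent Variables: coverage by Oregon's Medicaid program.
- Analysis Plan: "Time to Event: to determine association of coverage loss with sociodemographic characteristics". No model, time origin, censoring rule or covariate coding is given.
- Independent Variables: a list headed as sociodemographic characteristics (age, sex, race, ethnicity, language, income relative to the poverty level, urbanicity) that also contains "history of a healthcare visit to a community health center included in the OCHIN network during the study period (2011-2013").
- Exclusion Criteria: "Missing information on urban/rural residency status (n=4,025) and/or family income (n=973"). Neither exclusion concerns the timing of visits.

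Other entries do fix such variables in time. The study of insurance disparities in low-income Latino patients takes age at the start of the study, and the study following uninsured patients requires a visit before the ACA. The adolescent entry sets no such limit on visits.

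**The concern.** A predictor in a time-to-event model should be known at the time it is used. Here the visit item is collected over the whole of follow-up, including time after the event. As written, an adolescent who loses coverage in mid-2011 and first visits a CHC in 2013 has a visit history. If the item is a fixed covariate, that person carries it from day 1. Someone covered for all three years has three covered years in which to make a visit. If visiting differs with and without coverage, the value assigned at time zero depends partly on when coverage ended.

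The project itself expects visiting to depend on coverage. Hypothesis 2 (Aim 2) predicts that newly insured patients will increase their CHC visits relative to uninsured patients. The IRB protocol's Background section says insurance facilitates access to care. Neither statement is about these adolescents, but both make an unchanged visit rate after loss an awkward assumption to rely on.

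At stake is one hazard ratio in a study meant to show which adolescents lose coverage. The other hazard ratios in the model can also shift, but only for covariates that are themselves related to visiting.

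**Working it through.** **The plan's own figure.** The entry gives no hazard ratio, event count, visit rate or power statement, so there is nothing to reproduce.

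**Inputs from the documents.** N = 51,988; window of 3 years (1 January 2011 to 31 December 2013); visits and coverage loss measured over the same window.

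**Assumed inputs, not in the documents.** Loss rate 0.3/year; visit rate while covered v_c = 0.20/year; visit rate after loss v_a varied. Loss never depends on visits, so the true hazard ratio is 1.

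**Step 1: how the bias arises.** For loss at time t,

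P(any visit in 3 years) = 1 − exp(−[v_c·t + v_a·(3 − t)]).

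Someone who never loses coverage has 1 − exp(−0.20 × 3) = 1 − exp(−0.60) = 0.451. For someone who loses coverage at t = 0.5 years:

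| v_a per year | Exponent | P(any visit) |
|---|---|---|
| 0 (post-loss visits not counted) | 0.10 + 0 = 0.10 | 0.095 |
| 0.10 | 0.10 + 0.25 = 0.35 | 0.295 |
| 0.20 (unchanged) | 0.10 + 0.50 = 0.60 | 0.451 |
| 0.30 | 0.10 + 0.75 = 0.85 | 0.573 |

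Only with an unchanged rate is the chance of being classed as visited the same for early losers and for those who stay covered.

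**Step 2: effect on the hazard ratio.** Cox model h(t|x) = h0(t)·exp(βx), with x = 1 for any visit in 2011-2013, fixed at time zero. Simulated estimates (range over runs with n = 20,000 or 51,988):

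| Visit rate after loss (0.20 while covered) | Estimated HR, true value 1 |
|---|---|
| 0.05 | 0.57 |
| 0.10 | 0.70-0.73 |
| 0.15 | 0.83-0.87 |
| 0.20 | 0.98-1.01 |
| 0.30 | 1.28-1.30 |
| post-loss visits dropped, covariate still fixed | about 0.42 |

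**Step 3: wider assumptions.** With N = 51,988 over 36 months, 30% or 60% losing coverage, 20% or 50% visiting within 36 months at the covered rate, and with or without variation between persons in visit rate:

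| Visit rate after loss relative to before | HR, fixed covariate |
|---|---|
| 0 | 0.40-0.49 |
| 0.5 | 0.68-0.77 |
| 0.75 | 0.86-0.91 |
| 1 | 0.99-1.03 |
| 1.5 | 1.19-1.34 |
| 2 | 1.34-1.68 |

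With ratio 1, 45-56% of visited losers had their first visit after the loss, yet no bias appeared. In a separate set of runs (50% losing coverage, 30% visiting), the null was rejected in 3.5% of 200 runs with an unchanged rate, against a nominal 5%. With a rate only 10% lower after loss, it was rejected in 89% of 100 runs.

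**Step 4: the remedies.** Over all 48 scenarios, a time-dependent covariate (exposed only from the first visit before loss) gave 0.96-1.04. A covariate from an assumed 12 months before follow-up gave 0.96-1.05.

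**The case against.** **Post-loss visits do no harm by themselves.** A reader might infer that counting them as history is enough to create an association. It is not: with visiting unchanged and recorded through 2013 for everyone, the hazard ratio stays at about 1. Bias needs a change in visiting or in visit capture at loss, and the documents report neither for this cohort. This stands, and the point is conditional on it.

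**Fixed coding is inferred.** The entry says only that the analysis is time to event. The SAS program it names is not reproduced, and the program and dataset names suggest some handling of coverage gaps that cannot be seen. A reader might infer that the published hazard ratio is wrong. The documents show that the stated definition permits the error, not that it was made.

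**The direction is unknown.** A reader might infer that CHC contact was made to look protective. The general statement that insurance facilitates access points that way. But the same Background section describes CHCs as safety-net providers and reports that 36% of their patients were uninsured in 2012, so visits may rise after loss. Neither sign can be claimed.

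**The scope is small.** The item is one descriptor in one published paper, whose window ends before the 2014 expansion. Its code sits in a folder for IMPACCT, which the Medicaid data request lists as a separate approved study. This limits the weight of the point but does not answer it.

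**Conclusion.** The concern holds in conditional form. The visit covariate and the outcome share the 2011-2013 window, and nothing restricts visits to those before the loss. If the covariate is fixed, and if losing coverage alters visiting or its capture, the hazard ratio is biased with no true association. Its size under the assumed rates is about 0.7 if visiting halves after loss and about 1.3 if it rises by half. With nearly 52,000 subjects, even a 10% fall would usually be reported as a significant association.

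Three things are not established: that the covariate was coded as fixed, that visiting changed at loss, and in which direction. The documents give no loss or visit rates, so the figures show what is possible and do not estimate the error in the paper. Nothing here bears on Aims 1-3.

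**What to change.** Check the SAS program named in the entry. If visit history was already time-dependent or limited to visits before entry, say so in the entry; nothing more is needed. If it is fixed over 2011-2013, refit in one of two ways and report any change in the hazard ratios:

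1. a time-dependent covariate that switches from 0 to 1 at the first visit before coverage loss; or
2. a covariate defined from visits before each subject's entry, with follow-up starting at entry.

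Do not simply delete post-loss visits while keeping the covariate fixed. That gave the largest bias of any option examined (about 0.4).

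The cost is a small refit and, since the paper is published, a note on any change. It needs visit dates, and their availability for this dataset must be confirmed. The OCHIN-OHSU data use agreement for PACE covers 1 January 2012 to 31 December 2017 (Exhibit A, Time Period) and so omits 2011. Other entries use OCHIN patients from 2008-2011, so earlier records probably exist, but no section says so for this study. The pre-entry version also needs look-back data and will class fewer subjects as having a visit.

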where Y_{ijkt} represents individual i 's performance on an outcome measure of interest (i.e., insurance coverage,) nested within the j th clinic in state k at time t ; M_k represents a dummy variable taking a value of 1 in expansion-state and zero otherwise; and τ_t is a dummy variable taking a value of 1 if the observation took place after Medicaid expansion and 0 otherwise, Z_{ijkt} is a matrix of potential individual, clinic, or state confounders and f represents a general function that captures our intent to model a variety of outcome types through generalized linear mixed models (GLMMs).¹⁷³ The coefficient α is an overall intercept representing average baseline performance for all individuals; β represents the incremental baseline performance differential between clinics in expansion and non-expansion states and γ represents the change in performance pre- and post-expansion for all clinics. The coefficient of interest θ captures the relative performance improvement in outcomes for the patients in expansion versus non-expansion states over time. In this model, non-expansion states will serve as the reference. This equation is very general but can be adapted to include dummy variables for each time period or a continuous variable to capture linear time trends.

To address Aims 2 and 3, we can use a modification of the equation presented above. For **Aim 2**, the indicator M_k will be replaced with two indicator variables to represent the three insurance groups (newly insured, already insured, and uninsured) of interest. For **Aim 3**, the indicator M_k will be substituted by a binary variable denoting newly insured versus already insured. This equation can also be adapted to have the clinic serve as the unit of measurement instead of the individual. There are multiple options for estimating our DID approach. Our preferred method is to implement state random effects in clinic-level analyses and both clinic and state random effects in patient-level analyses to control for correlation of observations nested in clusters (e.g., individuals nested in clinics which are nested in states). Clinics and

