Dependent Variables	Insurance coverage in EHR.
Covariates	NA
Analysis Plan	NA
Data Set Name	NA
Code Location	NA

The Impact of the Affordable Care Act Medicaid expansion on visit rates for a patient population with diabetes or pre-diabetes in safety net health centers

Full Citation	[name], N., R. Springer, M. Marino, H. Angier, M. Hoopes, H. Holderness and J. E. DeVoe. (2018) The Impact of the Affordable Care Act Medicaid expansion on visit rates for a patient population with diabetes or pre-diabetes in safety net health centers. J Am Board Fam Med. 31(6):905-916
Objective	To compare clinic-level uninsured, Medicaid-insured, and privately insured visit rates within and between expansion and non-expansion states prior to and after the ACA Medicaid expansion among the three cohorts of patient populations; and, to assess whether there was a change in clinic-level overall, primary care, preventive care visits, and diabetes screening rates in expansion versus non-expansion states from pre- to post-ACA Medicaid expansion.
Study Population	198 primary care community health centers: Non-pregnant patients aged 19-64 with ≥1 ambulatory visit between 01/01/2012-12/31/2015 (n=483,912 in expansion states; n=388,466 in non-expansion states).
Exclusion Criteria	Pregnant women
Independent Variables	Expansion status
Dependent Variables	1. Insurance coverage 2. Healthcare services
Covariates	Health insurance status, sociodemographic variables, urban/rural, state-level factors.
Analysis Plan	
 • Rate Ratios • Difference in Difference • GEE/Poisson models with sandwich variance estimators • Clustered models by CHC

	
 • Exchangeable covariance structure • Sensitivity analysis
Data Set Name	STATES, ELIGIBLE FACILITIES, ENCOUNTERS_AV1215_pipe, PAT_CONSORT_08312016, FAC_URBRUR
Code Location	BOX at OHSU

Prescription Opioid Use Patterns, Use Disorder Diagnoses, and Addiction Treatment Receipt after the 2014 Medicaid Expansion

Full Citation	Springer, R., M. Marino, S. Bailey, H. Angier, J. O’Malley, M. Hoopes, S. Lindner, J. DeVoe and N. [name]. Prescription Opioid Use Patterns, Use Disorder Diagnoses, and Addiction Treatment Receipt after the 2014 Medicaid Expansion. Resubmitted 12/18 to Addiction.

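### The diabetes and pre-diabetes difference-in-differences clusters its variance by CHC although expansion is set by state, so its intervals are too narrow if residual changes differ between states

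*Combined protocol and SAP*

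**What the plan says.** The diabetes and pre-diabetes entry covers 198 CHCs ("n=483,912 in expansion states; n=388,466 in non-expansion states"). One of its objectives is to assess "whether there was a change in clinic-level overall, primary care, preventive care visits, and diabetes screening rates in expansion versus non-expansion states". Its Analysis Plan lists a difference-in-differences with "GEE/Poisson models with sandwich variance estimators", "Clustered models by CHC", "Exchangeable covariance structure" and "Sensitivity analysis"; the last is not described. State enters only through the covariates: "Health insurance status, sociodemographic variables, urban/rural, state-level factors". The entry does not say which states contribute, how the 198 CHCs split between the two groups, or how many CHCs each state has.

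In SAP B.4.4 the exposure is indexed by state: "M_k represents a dummy variable taking a value of 1 in expansion-state and zero otherwise". The same section names intra-state correlation as something the models should handle, prefers state random effects in clinic-level analyses, and proposes fixed-effects models as a robustness check. Section 8 (Data Analysis) of the IRB protocol also sets state random effects for clinic-level analyses. The SAP paragraph on standard errors allows bootstrapping but does not name the resampling unit.

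**The concern.** A sandwich variance is valid when the clusters it sums over are independent. Clustering by CHC handles correlation within a CHC, and the exchangeable working structure also acts only there. Neither covers a change that all CHCs in one state share, such as a state budget decision, an enrolment drive or a change in coding. The contrast is between groups of states, so a shared state change feeds directly into the estimate, and adding CHCs within the state does not average it away.

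State-level covariates may shrink this component, but what is left stays out of the variance. A state random intercept would not be enough either: it absorbs level differences between states and largely cancels from a pre-post change. The relevant component is state by period, and no section of either document states such a term, state-level clustering or a state-level bootstrap.

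At stake are the width of the intervals and the error rate of the expansion contrast in this paper.

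**Working it through.** The documents give no standard error, interval or power for this paper, so there is no figure to reproduce. The check asks how far a CHC-clustered SE falls short for a given state share.

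**Inputs**
- 198 CHCs: from the entry.
- Split 124 versus 74 (assumed): 198 × 225/359 = 124, using the 225 and 134 CHCs under Data Sources.
- 10 versus 6 states (assumed): the states listed there, with Wisconsin as expansion.
- State sizes (assumed): either equal, or in proportion to Table 2 facilities. Those are 312 expansion (Oregon 121, Rhode Island 59) and 213 control (Florida 169), leaving out Alaska, Indiana and Nevada.
- ρ, the share of residual variance in CHC change that lies between states: not in the documents; 1%, 5% and 10% shown.
- Equal weight per CHC, and a nominal two-sided 5% test (both assumed).

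**Formula.** Set the total residual variance of CHC change to 1. For each group let H be the sum over states of (the state's share of that group's CHCs)².
- Reported variance: 1/124 + 1/74 = 0.02158.
- True variance: ρ(H_E + H_N) + (1 − ρ) × 0.02158.
- SE ratio = √(true/reported). Type I error = 2Φ(−1.96/ratio).

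**Values of H**
- Equal-sized states: 1/10 + 1/6 = 0.2667.
- Table 2 proportions: 0.2257 + 0.6426 = 0.8683, equivalent to about 4.4 equal expansion states and 1.6 equal control states.
- Florida at 40.5% of control CHCs: the other five control states have 44 facilities in Table 2, so with 74 control CHCs Florida has at least 30. H_N = (30² + 9² + 3² + 6² + 21² + 5²)/74² = 0.2725.

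**Worked case, ρ = 5%**
- Equal states: 0.05 × 0.2667 + 0.95 × 0.02158 = 0.03383; ratio √(0.03383/0.02158) = 1.25.
- Table 2: 0.05 × 0.8683 + 0.0205 = 0.06391; ratio 1.72.

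| Layout | SE ratio at ρ = 1%, 5%, 10% | Type I error |
|---|---|---|
| Equal-sized states | 1.06, 1.25, 1.46 | 6.3%, 11.8%, 18.0% |
| Florida 40.5% of controls, equal expansion states | 1.08, 1.35, 1.62 | 6.9%, 14.5%, 22.6% |
| Florida 40.5%, expansion CHCs as in Table 2 | 1.10, 1.45, 1.79 | 7.6%, 17.7%, 27.4% |
| Table 2 proportions in both groups | 1.18, 1.72, 2.22 | 9.7%, 25.5%, 37.7% |

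At ρ = 0 every ratio is 1.00. The second and third rows differ only in the expansion group, so concentration in Oregon and Rhode Island matters as well as Florida. With equal-sized states, 9 versus 4 states gives 1.08, 1.34 and 1.60; 11 versus 8 gives 1.04, 1.20 and 1.38.

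**Simulation.** A null two-period Poisson GEE with exchangeable structure and a CHC sandwich (4,000 runs per cell, assumed SD of clinic log change 0.2) rejected 5.7% at ρ = 0. At 1%, 5% and 10% it rejected 6.1%, 10.6% and 18.5% with equal states, and 9.4%, 25.6% and 37.2% with Table 2 proportions. This agrees with the formula.

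**Florida's patient share.** The five other control states have 8,047 + 16,461 + 13,155 + 39,726 + 11,383 = 88,772 patients in Table 2. If this paper's patients are a subset of Table 2, Florida supplies at least (388,466 − 88,772)/388,466 = 77.1% of its control patients. If Alaska (3,820) and Indiana (16,200) are also controls, the floor is 72.0%.

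**The case against.** The strongest reply is that the size has no anchor. The state share is unknown, the layouts are assumed, and at low shares with equal states little happens: the simulation gave 5.4% at a 0.5% share and 6.1% at 1%, against 5.7% at zero. That stands, and it is why the point is conditional. A reader might infer that the published intervals are known to be wrong; the documents do not show that.

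Next, the Analysis Plan is a short list summarising a paper, and its sensitivity analysis could have dealt with state. That is possible, but the stated variance rule is clustering by CHC and nothing listed changes it.

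Third, a reader might call this a breach of the SAP. That goes too far. The SAP says there are several ways to estimate the contrast, calls state random effects only its preferred method, and lets models be refined. It justifies random effects by variation in expansion across clinics and states, which can be read as covering state-varying effects. What the SAP does show is that intra-state correlation was recognised and that states were treated as random, so inference confined to these particular states is not the declared aim.

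Fourth, a reader might take Florida's 77% as its share of the diabetes controls. It is not: the denominator is all non-pregnant adults with at least one visit, while the entry analyses three cohorts, and Florida's share of any one of them is not bounded. Likewise, 40.5% is a floor only if there are 74 control CHCs and Table 2 facilities correspond to CHCs.

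Finally, a change peculiar to one large control state is also a problem of bias, which better standard errors do not remove. The SAP's study considerations already acknowledge unobserved changes over time.

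**Conclusion.** The concern holds in conditional form. The mechanism and direction are clear: any positive residual state share makes the CHC-clustered intervals too narrow in every layout tried. The size is uncertain. Between shares of 1% and 10%, the SE is understated by a factor of 1.06 to 1.46 if states are of equal size and 1.18 to 2.22 if they follow Table 2. These figures rest on the assumed split, number of states, equal CHC weights and range of shares.

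The finding is limited to the expansion versus non-expansion contrast in this one paper. It should be fixed, because the plan's own framework recognises correlation within states and the remedy uses data already in hand.

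**What to change.** For this paper's expansion contrast, report state-level inference in a supplementary re-analysis, using one of:
- a null-imposed wild cluster bootstrap at state level; or
- a state-by-period random effect, with t on (number of states − 2) degrees of freedom.

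Say plainly that both are only approximately calibrated with few, unequal states. In null simulations (1,000 runs per cell, five layouts, shares 0% to 10%), the bootstrap rejected 3.8% to 7.5% when applied to clinic log rate changes and 5.0% to 9.0% as a score bootstrap of the Poisson GEE. The random-effect version, fitted to clinic log rate changes, rejected 1.5% to 9.1%.

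Do not simply move the ordinary sandwich to state level. On clinic log rate changes with a normal critical value it rejected 8.3% to 38.0%. In a separate linear simulation in Table 2 proportions, with t on (states − 1) degrees of freedom, its nominal 95% intervals covered 84%, 73% and 70% at shares of 0%, 5% and 10%.

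Alongside, list the states and the CHCs per state, and say what the sensitivity analysis was. An estimate without Florida is an optional check on bias from one dominant control state, not a variance remedy. With six control states it leaves at most 44 control CHCs and 88,772 control patients on Table 2 counts, so it will be imprecise.

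The cost is a refit of a published analysis and wider intervals.
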